**Table 13 – Fludarabine Toxicity:**

	Common Happens to 21-100 subjects out of every 100	Occasional Happens to 5-20 subjects out of every 100	Rare Happens to < 5 subjects out of every 100
Immediate: Within 1-2 days of receiving drug	Fever, fatigue, weakness, pain, nausea, vomiting, anorexia, cough, dyspnea	Edema including peripheral edema, chills, rash, diarrhea, rhinitis, diaphoresis, malaise, abdominal pain, headache, back pain, myalgia, stomatitis, flu-like syndrome	Anaphylaxis, tumor lysis syndrome, dehydration*
Prompt: Within 2-3 weeks, prior to next course	Myelosuppression (anemia, neutropenia, thrombocytopenia), infection (urinary tract infection, herpes simplex infection, pneumonia, upper respiratory)	Weight loss, gastrointestinal bleeding, hemoptysis, paresthesia, allergic pneumonitis, bronchitis, pharyngitis, visual disturbance, hearing loss, hyperglycemia	Sinusitis, dysuria, opportunistic infections and reactivation of latent viral infections like Epstein- Barr virus (EBV), herpes zoster and John Cunningham (JC) virus (progressive multifocal leukoencephalopathy [PML]) L , EBV associated lymphoproliferative disorder, pancytopenia (can be prolonged), pulmonary hypersensitivity a (dyspnea, cough, hypoxia, interstitial pulmonary infiltrate), pulmonary toxicity (acute respiratory distress syndrome [ARDS], pulmonary fibrosis, pulmonary hemorrhage, respiratory distress, respiratory failure), pericardial effusion, skin toxicity (erythema multiforme, Stevens-Johnson syndrome, toxic epidermal necrolysis, pemphigus), liver failure, renal failure, hemorrhage, transfusion-associated graft-versus-host disease has occurred following transfusion of nonirradiated blood products, phlebitis*, sleep disorder*, cerebellar syndrome*, depression*, mentation impaired*, alopecia*, pruritus*, seborrhea*, esophagitis*, constipation*, mucositis*, dysphagia*, hesitancy*, cholelithiasis*, abnormal liver function tests*, osteoporosis*, arthralgia*, abnormal renal function test*, proteinuria*, epistaxis*, hemorrhagic cystitis*, eosinophilia*
Delayed:			Neurotoxicity (increased with high doses): seizures, agitation, confusion, weakness, visual

THIS PROTOCOL IS FOR RESEARCH PURPOSES ONLY, SEE PAGE 1 FOR USAGE POLICY

Any time later during therapy, excluding the above conditions			disturbances, optic neuritis, optic neuropathy, photophobia, blindness, paralysis, coma, death, peripheral neuropathy a ; autoimmune phenomena: thrombocytopenia/thrombocytopenic purpura (ITP), Evans syndrome, hemolytic anemia, acquired hemophilia
Late: Any time after completion of treatment			Myelodysplastic syndrome/acute myeloid leukemia (mainly associated with prior or concomitant or subsequent treatment with other anticancer treatments), skin cancer (new onset or exacerbation)
Unknown Frequency and Timing:	Pregnancy Category D Based on its mechanism of action, fludarabine phosphate can cause fetal harm when administered to a pregnant woman. Fludarabine phosphate was embryolethal and teratogenic in both rats and rabbits.		

(L) Toxicity may also occur later.

\* Reported in ≤ 3% of subjects. Since these are not considered life threatening they are not included in the consent.

a These effects were not reported in children.

### Formulation and Stability:

Fludarabine phosphate injection is available as sterile lyophilized powder and in solution. Each single-dose vial of powder contains 50 mg of the active ingredient fludarabine phosphate, 50 mg of mannitol, and sodium hydroxide to adjust the pH to 7.7. After reconstitution, the pH range for the final product is 7.2-8.2. The single-dose solution vial contains 25 mg/mL, 2 mL of fludarabine phosphate. It may contain mannitol and is preservative-free.

Fludarabine phosphate vials should be stored refrigerated at 2-8°C (36-46°F).

### Guidelines for Administration:

See Treatment and Dose Modification sections of the protocol.

Fludarabine phosphate powder should be reconstituted with 2 mL of Sterile Water for Injection. The solid cake should fully dissolve in 15 seconds or less. The resulting concentration is 25 mg/mL. When reconstituted to a final concentration of 25 mg/mL, the drug is stable for at least 16 days at room temperature and normal light conditions. The manufacturer recommends that the solution be used within 8 hours after reconstitution.

Prior to administration, fludarabine 25 mg/mL solution or the reconstituted 25 mg/mL solution should be further diluted in 100 mL or 125 mL of D5W or NS. Concentrations of 0.25 to 1 mg/mL have been used in clinical trials. When diluted to a final concentration of 1 mg/mL, fludarabine is stable for at least 16 days at room temperature and normal light conditions. The manufacturer recommends that the diluted solution be used within 8 hours after preparation. Parenteral drug products should be inspected visually for particulate matter and discoloration prior to administration.

### Supplier:

Commercially available from various manufacturers. See package insert for further information.

THIS PROTOCOL IS FOR RESEARCH PURPOSES ONLY, SEE PAGE 1 FOR USAGE POLICY

THIS PROTOCOL IS FOR RESEARCH PURPOSES ONLY, SEE PAGE 1 FOR USAGE POLICY

## 9.4 Intrathecal Triples

(08/03/21)

(Methotrexate/Hydrocortisone/Cytarabine, IT-3)

### Source and Pharmacology:

The intrathecal route of administration of a drug produces more consistent CSF drug concentrations at relatively smaller doses because of the volume difference between the CSF and blood compartments (140 mL vs. 3500 mL in an adult). (The CSF volume of children after the first 3 years is equivalent to that of an adult). Drug half-lives are longer as well because clearance is related to flow rather than metabolism or protein binding. Intrathecal methotrexate has a biphasic elimination curve from the CSF with a  $t_{1/2}$  of 4.5 and 14 hours respectively. Following IT injection of cytarabine the elimination of the drug from the CSF is biphasic with a  $t_{1/2}$  of 1 and 3.4 hours respectively which is 8-fold longer than the clearance from plasma. The elimination of hydrocortisone is similarly prolonged.

**Table 14 - Intrathecal Triple Therapy (Methotrexate/Hydrocortisone/Cytarabine) Toxicity:**

	Common Happens to 21-100 children out of every 100	Occasional Happens to 5-20 children out of every 100	Rare Happens to < 5 children out of every 100
Immediate: Within 1-2 days of receiving drug	Nausea, vomiting, fever, headache	Arachnoiditis: (headache, fever, vomiting, meningismus and pleocytosis)	Rash, anaphylaxis (L), paresis, bleeding into subarachnoid or subdural space (risk > with platelet counts <20,000), confusion, fatigue, disorientation, seizures
Prompt: Within 2-3 weeks, prior to the next course			Myelosuppression, somnolence, ataxia, cranial nerve palsy, transient and rarely permanent paraplegia (L), speech disorders
Delayed: Any time later during therapy, excluding the above condition		Cognitive disturbances (L), learning disabilities (L)	Demyelating leukoencephalopathy  (L), blindness 
Late: Any time after the completion of treatment			Progressive CNS deterioration 

 May be enhanced by systemic therapy such as high dose methotrexate or cytarabine and/or cranial irradiation.

(L) Toxicity may also occur later.

### Formulation and Stability:

Methotrexate 25 mg/mL **preservative free** 2 mL vial or methotrexate 20 mg preservative free sterile powder for injection vial. Cytarabine 100 mg preservative free sterile powder for injection. Hydrocortisone sodium succinate 100 mg vial sterile powder for injection.

### Guidelines for Administration:

See Treatment and Dose Modification sections of the protocol.

For intrathecal administration, dilute each agent with 5-10 mL preservative free NS, lactated ringers or Elliot's B solution or as per institutional standard of practice. The volume of CSF removed should be equal to at least half the volume delivered.

THIS PROTOCOL IS FOR RESEARCH PURPOSES ONLY, SEE PAGE 1 FOR USAGE POLICY

**Table 15 – Methotrexate Dosing Guidelines by Age**

Patient Age (years)	Recommended volume	10% CSF volume	CSF Volume *
0 < 1 year	5-10 mL	5 mL	50 ± 10 mL (babies)
≥ 1 to < 2 years	5-10 mL	5 mL	50 ± 10 mL (babies)
≥ 2 to < 3 years	5-10 mL	8 mL	80 ± 20 mL (younger children)
≥ 3 to < 9 years	5-10 mL	10 mL	100 ± 20 mL (older children)
≥ 9 years	5-10 mL	13 mL	130 ± 30 mL (adults)

\*Rieschelbach, R.E. et.al. Subarachnoid distribution of drugs after lumbar injection. *N Engl J Med* 1962 Dec 20; 267:1273-8

Of note: Larger volumes approximating at least 10% of the CSF volume, isovolumetric delivery, with the patient remaining prone after the procedure may facilitate drug distribution. These procedures have not been validated in clinical trials. They are allowed but not mandated for patients on COG studies.

Intrathecal triples are stable in NS for 24 hours at 25°C but contain no preservative and should be administered as soon as possible after preparation.

**Supplier:**

Commercially available from various manufacturers. See package insert for further information.

**9.5 Leucovorin Calcium**

(05/07/19)

(LCV, Wellcovorin®, citrovorum factor, folinic acid, Calcium folinate) NSC #003590

**Source and Pharmacology:**

Leucovorin is a mixture of the diastereoisomers of the 5-formyl derivative of tetrahydrofolic acid (THF). The biologically active compound of the mixture is the (-)- l-isomer, known as Citrovorum factor or (-)-folinic acid. Leucovorin does not require reduction by the enzyme dihydrofolate reductase in order to participate in reactions utilizing folates as a source of “one-carbon” moieties. Administration of leucovorin can counteract the therapeutic and toxic effects of folic acid antagonists such as methotrexate, which act by inhibiting dihydrofolate reductase. In contrast, leucovorin can enhance the therapeutic and toxic effects of fluoropyrimidines used in cancer therapy, such as 5-fluorouracil. Leucovorin is readily converted to another reduced folate, 5,10-methylenetetrahydrofolate, which acts to stabilize the binding of fluorodeoxyuridylic acid (an active metabolite of 5-FU) to thymidylate synthase and thereby enhances the inhibition of this enzyme. Peak serum levels of 5-methyl THF (an active metabolite) were reached at approximately 1.3-1.5 hours (IV/IM) and 2.3 hours for the oral form. The terminal half-life of total reduced folates was approximately 6.2 hours. Following oral administration, leucovorin is rapidly absorbed and expands the serum pool of reduced folates. At a dose of 25 mg, almost 100% of the l-isomer (the biologically active form) but only 20% of the d-isomer is absorbed. Oral absorption of leucovorin is saturable at doses above 25 mg. The apparent bioavailability of leucovorin was 97% for 25 mg, 75% for 50 mg, and 37% for 100 mg doses. Both oral and parenteral leucovorin raise the CSF folate levels.

THIS PROTOCOL IS FOR RESEARCH PURPOSES ONLY, SEE PAGE 1 FOR USAGE POLICY

**Table 16 – Leucovorin Calcium Toxicity:**

	Common Happens to 21-100 children out of every 100	Occasional Happens to 5-20 children out of every 100	Rare Happens to < 5 children out of every 100
Immediate: Within 1-2 days of receiving drug			Anaphylaxis, urticaria, seizure
Unknown Frequency and timing:	Fetal toxicities and teratogenic effects of leucovorin in humans are unknown. It is unknown whether the drug is excreted in breast milk.		

### **Formulation and Stability:**

Leucovorin calcium for injection is supplied as a sterile ready to use liquid and a sterile powder for injection. The 10 mg/mL preservative free liquid is available in 50 mL vials containing sodium chloride 400 mg/vial. Store preservative free liquid in the refrigerator at 2°-8°C (36°-46°F) protected from light. The powder for injection is available in 50 mg, 100 mg, 200 mg, and 350 mg vials. Store at room temperature 15°-25°C (59°-77°F) protected from light. Reconstitute the sterile powder with sterile water for injection or bacteriostatic water for injection to a concentration of 10 mg/mL leucovorin calcium. **Do not use diluents containing benzyl alcohol for doses > 10 mg/m^2 or in infants < 2 years of age or patients with allergy to benzyl alcohol.** When Bacteriostatic Water is used, the reconstituted solution is good for 7 days. If reconstituted with SWFI, use solution immediately as it contains no preservative. One milligram of leucovorin calcium contains 0.004 mEq of leucovorin and 0.004 mEq of calcium.

The oral form of leucovorin is available as 5 mg, 10 mg, 15 mg, and 25 mg tablets. Inactive ingredients vary depending on manufacturer but tablet formulations may include: corn starch, dibasic calcium phosphate, magnesium stearate, pregelatinized starch, lactose, microcrystalline cellulose, and sodium starch glycolate.

### **Guidelines for Administration:**

See Treatment and Dose Modifications sections of the protocol.

#### Injection:

Because of the calcium content of the leucovorin solution, no more than 160 mg of leucovorin should be injected intravenously per minute (16 mL of a 10 mg/mL solution per minute). IV leucovorin and sodium bicarbonate are incompatible.

#### Oral:

Oral leucovorin should be spaced evenly (e.g., every six hours) throughout the day and may be taken without regard to meals. Doses > 25 mg should be given IV due to the saturation of absorption.

THIS PROTOCOL IS FOR RESEARCH PURPOSES ONLY, SEE PAGE 1 FOR USAGE POLICY

Leucovorin should not be administered < 24 hours after intrathecal injections which contain methotrexate unless there are special circumstances.

**Supplier:**

Commercially available from various manufacturers. See package insert for further information.

## 10.0 CRITERIA FOR REMOVAL FROM PROTOCOL THERAPY AND OFF STUDY CRITERIA

### 10.1 Criteria for Removal from Protocol Therapy

- a) Treatment failure (See [Appendix VIII](#) for definitions).
- b) Adverse Events requiring removal from protocol therapy (See [Section 6.1](#), [Section 6.2](#), and [Section 6.3.1](#))
- c) Refusal of protocol therapy by patient/parent/guardian
- d) Non-compliance that in the opinion of the investigator does not allow for ongoing participation.
- e) Completion of up to 2 cycles of therapy.
- f) Physician determines removal from protocol is in the patient's best interest.
- g) Repeat eligibility studies are outside the parameters required for eligibility prior to the start of GMI-1271 (Uproleselan) (See [Section 8.1](#)).
- h) Study is terminated by Sponsor.
- i) Pregnancy
- j) Development of secondary malignancy
- k) Patient receives concurrent cancer therapy that is not part of protocol therapy (See [Section 7.1](#))

**Patients who are removed from protocol therapy during Cycle 1 should continue to have the required observations in [Section 8.1](#) until the originally planned end of the cycle or until all adverse events have resolved per [Section 13.5](#) whichever happens LATER. The only exception is with documentation of the patient's withdrawal of consent. Patients who are removed from protocol therapy in subsequent cycles should have the necessary observations to ensure adequate clinical care.**

Patients who are off protocol therapy are to be followed until they meet the criteria for Off Study ([see below](#)). Ongoing adverse events, or adverse events that emerge after the patient is removed from protocol therapy, but within 30 days of the last dose of investigational agent, must be followed and reported via RAVE and CTEP-AERS (if applicable). Follow-up data will be required unless consent is withdrawn.

### 10.2 Off Study Criteria

- a) Thirty days after the last dose of the investigational agent
- b) Withdrawal of consent for any required observations or data submission.
- c) The patient does not receive protocol treatment after study enrollment.
- d) Patient enrollment onto another COG study with therapeutic (anti-cancer) intent.
- e) Lost to follow-up
- f) Death

THIS PROTOCOL IS FOR RESEARCH PURPOSES ONLY, SEE PAGE 1 FOR USAGE POLICY

## 11.0 STATISTICAL AND ETHICAL CONSIDERATIONS

### 11.1 Sample Size and Study Duration

The study will require a minimum of 4 DLT-evaluable patients and a maximum of 12. Once the MTD or recommended Phase 2 dose has been defined, up to 6 additional patients with recurrent or refractory AML, t-AML, MDS, t-MDS or MPAL without restrictions on heme evaluability may be enrolled to acquire PK data in a representative number of young patients so that the study includes an approximately equal distribution of patients <12 years old and 12-17 years old. Therefore, the expected maximum number of patients required for the entire study will be 22 allowing for 6 evaluable patients at each of two dose levels, 20% inevaluability for DLT or for failure to contribute essential PK samples (for patients with weight  $\geq 10$  kg: pre-dose, 30 minutes and 2 hrs after the dose on days 1 and 6; for patients with weight <10 kg: pre-dose, 30 minutes and 1.5 hrs after the dose on days 1 and 6), and 6 additional patients for PK analysis at the MTD/RP2D. The absolute maximum will be 36 patients which would occur in the unlikely scenario that both dose levels expand to 12 due to DLTs of different classes (See [Section 11.2.2](#)).

The enrollment rate is expected to be about 1 patient per month based on previous COG early phase new agent studies for patients with AML. Therefore, the study may require up to 36 months to complete enrollment but is expected to be completed within about 22 months.

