### 11.3 Dose Evaluation and Determination of MTD

Up to six DLT-evaluable patients will be enrolled at DL1 in Part A. If 1 or fewer DLT-evaluable patients experience a Cycle 1 dose limiting toxicity, then DL1 will be the RP2D and up to six additional patients will be enrolled in Part B (PK cohort) at this dose level. If 2 or more patients experience a Cycle 1 DLT at DL1, then the maximum tolerated dose has been exceeded and DL-1 will open for enrollment. Further, if the Part B cohort opens at DL1 and the number of patients in Part A and Part B combined who experience a Cycle 1 dose limiting toxicity exceeds 33%, then the maximum tolerated dose has been exceeded and DL-1 will open for enrollment. Up to six DLT-evaluable patients will be enrolled at DL-1. If 1 or fewer DLT-evaluable patients experience a Cycle 1 dose limiting toxicity at DL-1, then DL-1 will be the MTD/RP2D and up to six additional patients will be enrolled in Part B (PK cohort) at this dose level. If 2 or more patients experience a Cycle 1 DLT at DL-1, then the maximum tolerated dose has been exceeded and the study will close to accrual. Further, if the Part B cohort opens at DL-1 and the number of patients at DL-1 in Part A and Part B combined who experience a Cycle 1 dose limiting toxicity exceeds 33%, then the maximum tolerated dose has been exceeded and the study will close to accrual. See exceptions to rule in Section 11.2.2 for defining the MTD.

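### Section 11.1's absolute maximum of 36 counts one PK cohort, but Section 11.3 can open two, so the plan's own rules allow about 44–45 enrolled

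*Combined protocol and SAP*

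**What the plan says.** Section 11.1 (Sample Size and Study Duration) opens: "The study will require a minimum of 4 DLT-evaluable patients and a maximum of 12". It then builds an expected maximum of 22, "allowing for 6 evaluable patients at each of two dose levels", plus "6 additional patients for PK analysis at the MTD/RP2D", with "20% inevaluability for DLT or for failure to contribute essential PK samples". The upper limit follows: "The absolute maximum will be 36 patients which would occur in the unlikely scenario that both dose levels expand to 12", through the exception in Section 11.2.2. At about one patient per month, Section 11.1 turns 36 patients into up to 36 months, and Table 17 (Planned Enrollment Report) also totals 36.

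Section 11.3 sets the enrolment path. Up to six DLT-evaluable patients enter Part A at DL1. With one DLT or none, up to six more enter Part B at DL1. The next step begins "Further, if the Part B cohort opens at DL1 and the number of patients in Part A and Part B combined": if those with a Cycle 1 DLT exceed 33%, the MTD has been exceeded and DL-1 opens for up to six. With one DLT or none there, "then DL-1 will be the MTD/RP2D and up to six additional patients will be enrolled in Part B (PK cohort" at DL-1.

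Section 11.2.2 counts Part B DLTs towards the MTD. It also lets a dose level grow from six to 12 when two of six patients have DLTs of different classes and further conditions hold.

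**The concern.** Section 11.1 allows for six PK patients once. Section 11.3 provides for up to six at DL1 and, after a de-escalation triggered by Part B, up to six more at DL-1. The two sections therefore describe different maxima. The ceiling of 12 DLT-evaluable patients also sits in the same paragraph as a scenario in which both levels reach 12, which is 24 in dose finding alone.

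At stake is the stated limit on the number of children enrolled in a study of an agent with no earlier pediatric studies (Section 2.4), with the study duration and Table 17 that rest on it. On the longest permitted path, the trial would pass its stated limit after a safety-driven de-escalation, with the DL-1 dose-finding and PK cohorts unfinished.

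**Working it through.** **Inputs.** Six per dose level, two levels, one PK cohort of six, 20% inevaluable, 22 and 36 stated (Section 11.1). Expansion from six to 12 per level (Section 11.2.2). Up to six in Part B at each of DL1 and DL-1 (Section 11.3).

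**The plan's figures, reproduced**
- Expected maximum: (6+6+6) × 1.2 = 21.6, rounded up to 22.
- Absolute maximum: (12+12+6) × 1.2 = 36.
- Dose finding: 6+6 = 12.

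The match is exact with one PK cohort and an allowance of n × 1.2. Dividing by 0.8 instead gives 18/0.8 = 22.5 (23) and 30/0.8 = 37.5 (38).

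**With both Part B cohorts counted**

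| Path | Patients | × 1.2 | ÷ 0.8 | Stated |
|---|---|---|---|---|
| No expansion | 6+6+6+6 = 24 (12 dose finding, 12 PK) | 28.8 (29) | 30 | 22 |
| One level expanded | 12+6+6+6 = 30 | 36 | 37.5 (38) | – |
| Both levels expanded | 12+6+12+6 = 36 (24 dose finding, 12 PK) | 43.2 (44) | 45 | 36 |

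At one patient per month, the last row means 44–45 months rather than 36.

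**How likely is the branch without expansion?** DL1 must show at most 1/6 DLTs in Part A and then at least 4/12 in Parts A and B combined (4/12 exceeds 33%). With X_A and X_B binomial on six patients each, at an assumed true DLT rate p:

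A(p) = P(X_A=0)·P(X_B≥4) + P(X_A=1)·P(X_B≥3).

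At p = 20%: 0.2621 × 0.0170 + 0.3932 × 0.0989 = 0.043.

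| p at DL1 | 10% | 20% | 30% | 40% |
|---|---|---|---|---|
| A(p) | 0.6% | 4.3% | 8.6% | 9.3% |
| A(p), and Part B also opens at DL-1 (rate there assumed half of p) | 0.6% | 3.8% | 6.7% | 6.1% |

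These are upper bounds for using all 24 places, because Part B can stop before six are enrolled.

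**Does that branch fit under 36?** If each of 36 enrolled patients is evaluable with probability 0.8, the chance of at least 24 evaluable is 98%.

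**How likely is the path with both expansions?** DL1 must go 2/6, then at most 3/12, then at least 6/18 after Part B. DL-1 must then go 2/6 and at most 3/12. The DL1 part equals P(2 of 6) × A(p), because the six patients added by expansion and the six in Part B must meet the same two conditions as in A(p). With q the rate at DL-1:

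P(2 of 6; p) × A(p) × P(2 of 6; q) × P(at most 1 of 6; q).

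- p = q = 30%: 0.3241 × 0.0856 × 0.3241 × 0.4202 = 0.4%.
- p = 40%, q = 20%: 0.3110 × 0.0934 × 0.2458 × 0.6554 = 0.5%.

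Over p from 10% to 40%, with q equal to p or half of it, the result is about 0.5% or less. This is before the other conditions of Section 11.2.2.

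**The case against.** The strongest defence is that the plan's numbers are adequate in practice. Section 2.5.2 does not expect toxicity to be what sets the recommended dose. Expansion under Section 11.2.2 is discretionary and needs different toxicity classes, reversibility and agreement of all named parties. This stands as far as likelihood goes. It does not rescue the label: Section 11.1 already defines its absolute maximum by a path it calls unlikely, so another path written into the decision rules cannot be left out.

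A reader might infer more than the documents support:

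- *That 24 patients is the routine requirement, or that 22 is a breached cap.* It is a low-probability branch, and 22 is labelled an expected maximum, a planning figure.
- *That the trial would run out of places whenever DL1 fails in Part B.* Without expansion that branch needs about 29–30 enrolled and fits under 36. With one expansion it needs 36 on the plan's own allowance and 38 on division by 0.8. Only with both expansions is 36 clearly exceeded.
- *That 24 DLT-evaluable patients are needed without expansion.* Twelve are dose-finding patients and 12 are PK patients. The PK cohort is enrolled without restriction on hematological evaluability and is replaced for missing PK samples. Counting its DLTs does not make it a DLT-evaluable cohort.
- *That multiplying by 1.2 is itself the fault.* No formula is stated, and the choice changes the totals by one or two patients.

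One could also read 36 as 12+6+12+6, with both PK cohorts in it. It then leaves nothing for the 20% inevaluability that Section 11.1 says it allows, so it is still not a maximum.

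**Conclusion.** Sections 11.1 and 11.3 disagree on how many PK cohorts can open. Under the plan's own rules 36 is not an absolute maximum: both expansions with both Part B cohorts give 36 patients before the inevaluability allowance and 44–45 after it, an excess of 8–9. Without expansion the rules allow 29–30 enrolled, above the expected maximum of 22 but within 36. The figure of 12 DLT-evaluable patients is right only when no level expands; otherwise dose finding can reach 24.

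The practical risk is small: about 0.6–9% for the branch without expansion and about 0.5% or less for the longest path. Both rest on assumed DLT rates of 10–40% and independent patients, since the plan gives no DLT rate. Nor is 44–45 a strict ceiling. Replacement has no stated cap (Sections 11.2.1 and 11.2.2), and the Dose Level 2 that Section 5.3.1 says may be considered is in no count.

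**What to change.** Reconcile Section 11.1 with Section 11.3 in one of two ways.

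1. Keep the rules and restate Section 11.1: up to 12 dose-finding patients (24 if both levels expand), about 29–30 enrolled if Part B opens at both levels without expansion, and about 44–45 enrolled as the maximum. Update the 36-month duration and the Table 17 total.
2. Keep the lower totals and state in Section 11.3 that PK-cohort enrolment is limited to six in total across dose levels. The figures are then about 22–23 and 36–38, depending on the allowance formula. Section 11.1 still needs to say that 12 becomes 24 if both levels expand.

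Either way, state that the totals assume 20% inevaluability and no Dose Level 2, because replacement is uncapped.

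The first option costs wording and a revised Table 17, with less favourable headline numbers but no patient whom the rules do not already allow. The second costs one sentence, but if Part B is used up at DL1, PK data at DL-1 would come only from its dose-finding patients.
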